c) Frailty assessment: Individuals identified as frail (approximately 10% of the community-dwelling older adult population) ([name] and Hazuda, 2008) will be excluded. Pre-frailty is defined as the presence of 1 or 2 of: 1) self-reported unintentional weight loss of 10 lbs or more in last year, 2) self-reported exhaustion, 3) low physical activity based on the Minnesota Leisure Time Physical Activity Questionnaire, 4) weak hand grip, 5) and slowness on 10-foot walk at usual pace. These measures have been standardized in SALSA, and will be used in this study as described ([name] and Hazuda, 2008). Non-frailty is defined as the presence of 0 characteristics. Frailty will be assessed every 6 months using the Fried criteria. If a participant's frailty category or score worsens based on Fried criteria (Fried et al., 2001), it will be repeated in 3 months and then at the 6 months intervals as per the protocol thereafter. At the baseline, self-reported unintentional weight loss will be used as criteria for weight loss as stated above. However, at all subsequent visits, individuals who have lost  $\geq 5\%$  of their baseline weight will be considered to have met the criteria for weight loss. As a measure of lower extremity function, we will use the Short Physical Performance Battery (SPPB) (Guralnik et al., 1994) and the 6-Minute Walk Test (6-MWT) (Harada et al., 1999). Both the SPPB and the 6-MWT are assessments of physical function commonly used in geriatrics studies. Lower extremity strength will be measured every 6 months with a knee extension dynamometer chair. The participants will be positioned in an upright position, with the ankle to a force or torque transducer at the knee angle of  $90^\circ$ . After 3 warm-up trials, 3 trials will be conducted to measure maximal voluntary contraction force of the knee extension muscle. We will also screen for depression using the Geriatric Depression Scale (Yesavage et al., 1982) and cognitive

impairment using the Mini Mental State Examination (Folstein et al., 1975) as part of the frailty assessment.

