**Follow up visits.** History/physical exam will be conducted every 6 months. Fasting glucose measurement and HbA1c will be conducted every three months, and OGTT will be conducted every 6 months. However, if fasting glucose and/or the HbA1c suggest conversion to diabetes based on American Diabetes Association criteria, OGTT will be performed. Assays of systemic inflammation (in plasma) will be conducted every 6 months. Insulin clamp with muscle biopsies will be conducted at 12 and 24 months, such that the treatment effect on tissue inflammation and insulin signaling may be determined. The table below outlines the follow up visits and procedures. A grace period of +/- 3 weeks is provided to complete follow-up visits.

Study visits and procedures															
Visit #	1	2	3	4	5	***6	7	8	9	***10	11	***12	13	14	15
Year	1												2		
Month	Screening Visit	0	1	3	6	9	12	12	12	15	18	21	24	24	24
Time Interval		3-21* Days	5-7 Days	2.5 Mo	3 Mo	3 Mo	3 Mo	3-21 Days	5-7 Days	2.5 Mo	3 Mo	3 Mo	3 Mo	3-21 Days	5-7 Days
History & Physical, with Frailty Assessment	X			X	X		X				X		X		
Biodex	*X				*X		*X			*X			*X		
Activity monitor		X							X						X
Quality of life assessment	X			X	X		X				X		X		
EKG	X						X								X
Urinalysis	X						X								X
OGTT	X				X		X				X		X		
Safety labs	X			X	X	X	X			X	X	X	X		
HbA1c	X			X	X	X	X			X	X	X	X		
Coagulation tests	X						X								X
Systemic inflammation		*X			X			*X			X				*X
DEXA		*X							*X						*X
Stool collection		*X							*X						*X
Insulin clamp w/ biopsy		*X							*X						*X
Examination of biopsy site			**X							**X					**X

\*These visits may be done at other approximate visits to reduce the amount of exposure to the participant due to COVID-19.

\*\*Due to COVID-19, the participants can opt to do this visit via phone or in person.

\*\*\*Due to COVID-19, if the participants do not need to do the Frailty assessment, this visit can be done via phone. Labs may be performed at the Quest Diagnostics laboratory nearest to the participant instead of the research unit.

**Urinalysis (UA) will be repeated if needed prior to starting on pioglitazone (only for subjects who convert to diabetes and do not have adequate glycemic control on metformin alone).**

**Basic metabolic panel (kidney function) will be performed as needed to check kidney function at least 48 hours after any radiologic exam using contrast dye.**

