#### Data Analysis Plan:

### STATISTICAL METHODS & POWER CALCULATIONS

**Overview.** In all analyses for Aim 1 and Aim 2, primary inference will be drawn based on intention to treat (ITT) analyses. Average complier effect (ACE) will be used to inform the metformin effect under full compliance to treatment assignments (Angrist et al, 1996). Per protocol analyses will be used to inform the metformin effect among completers. All analyses will be carried out unadjusted and with adjustment for covariates (Table 7) and covariate interactions with treatment and time. Corrections for multiple comparisons will be applied as appropriate.

The impact of metformin treatment on the progression of frailty status (non-frail, pre-frail, frail) over time will be assessed with a repeated measures mixed effects multinomial logistic model that models the log-odds of adjacent frailty statuses in terms of an indicator of metformin use, time, and the metformin use by time interaction. The possibility of non-linear trends of the log-odds of frailty statuses will be assessed by including an additional time factor (e.g., time squared) and its interaction with metformin use. The best fitting model will be used for inference. Secondary outcomes including gait speed, 6 minute walk, SPPB, frailty index constructed from the research data collected according to the Rockwood index (Searle et al., 2008; Rockwood et al., 2007), and body composition will similarly assessed. Under the linear trend model, the beneficial impact of metformin will be revealed by a significant time by treatment interaction associated with the log-odds of frailty status progression, indicating that the rate of increase in the likelihood of frailty progression over time is reduced in the metformin arm relative to the placebo arm. Under the non-linear trend model, the impact of metformin will be revealed by a significant reduction in the log-odds of frailty status progression in the metformin arm versus placebo at certain time points during the follow-up. SAS proc **nlmixed** will be used in the mixed effects model analyses. Proc **nlmixed** is preferred over other mixed effects modeling procedures such as GEE because it is valid under missing at random (MAR) assumption, accommodates linear and non-linear modelling, and uses maximum likelihood estimation.

Table 7. Covariates included in statistical analyses

Categories of covariates	Baseline	Time Varying
Demographics (age, sex)	X	
BMI (obesity), sarcopenia	X	X

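### The Aim 1 success rule changes with the model the data select, and the non-linear rule names neither visits nor a correction, so the two-sided 5% level is not secured

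*Combined protocol and SAP*

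**What the plan says.** The Overview of Statistical Methods & Power Calculations analyses frailty status with "a repeated measures mixed effects multinomial logistic model". A further time term, with time squared given as an example, may be added together with its interaction with treatment. Then: "The best fitting model will be used for inference". No fit criterion is given.

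The success rule depends on the outcome of that choice:

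- Linear trend: "the beneficial impact of metformin will be revealed by a significant time by treatment interaction".
- Non-linear trend: "a significant reduction in the log-odds of frailty status progression in the metformin arm versus placebo at certain time points during the follow-up".

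The only multiplicity statement that covers Aim 1 is "Corrections for multiple comparisons will be applied as appropriate". Section 3.D.3 powers Aim 1 with two-sided testing at 5%. The overall type 1 error of 0.05 in 3.D.5 belongs to the Aim 2 calculation for TNFα.

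The assessments that feed the model are described in three ways:

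- Screening Tests, c) Frailty assessment: "Frailty will be assessed every 6 months using the Fried criteria", and after any worsening "it will be repeated in 3 months and then at the 6 months intervals as per the protocol thereafter".
- Study Procedures, k) Management of conversions: frailty is also measured at confirmed diabetes conversion, and the month-12 or month-24 assessment is dropped if it falls within one month of that.
- The study visits table: the row "History & Physical, with Frailty Assessment" is marked at screening and months 3, 6, 12, 18 and 24.

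**The concern.** A test holds its level when the rule for claiming success is fixed before the data are seen. Here the data pick the model and the model picks the rule. One branch is a single 1-df test. The other is a set of contrasts whose number and timing are open, with no stated family, method or split of alpha. If any one significant visit is allowed to count and nothing is corrected, metformin can be credited with an effect on frailty more often than 5% allows.

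The open schedule compounds this. Six-monthly assessment gives four follow-up points and the visits table gives five, so the size of any correction family is itself undecided. The triggered assessments depend on the outcome or on diabetes conversion, so whether they enter the model also matters.

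**Working it through.** **Inputs from the documents.** 60 completers per arm, two-sided 5% and 6 repeated measures (3.D.3); follow-up at months 3, 6, 12, 18 and 24 (visits table); linear and quadratic models and the two success rules (Overview).

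**Assumptions not in the documents.** AIC is the fit criterion; one significant follow-up visit is enough; no visit-level correction; five within-person covariance structures V (equal correlation 0.5, 0.65 or 0.8; or serial decay with one-year correlation 0.5 or 0.7 and 15% noise).

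**The plan's own figure.** The 86% power in 3.D.3 was not reproduced. Simulating its transition rates and fitting a random-intercept adjacent-category model gave 97-99% for the interaction test and 94-98% for an overall treatment effect. The tested coefficient, random effects and boundary rule are not stated, so this does not show that 86% is wrong. The error rates below do not use it.

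**Step 1, simple bounds.** For k independent tests at 5%, the chance of at least one false positive is 1 − 0.95^k: 1 − 0.95^4 = 18.6% and 1 − 0.95^5 = 22.6%. Visit contrasts from one fitted curve are strongly correlated, so the true figure is lower.

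**Step 2, large-sample calculation with no treatment effect.** Arm differences d at months 0, 3, 6, 12, 18 and 24 follow N(0, 2V/60). With W = (2V/60)⁻¹, the fit is b = (X′WX)⁻¹X′Wd, where X holds (1, t) or (1, t, t²). The visit contrast at t is (1, t, t²)b divided by its standard error.

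The quadratic model adds two parameters, so AIC picks it when LR > 2 × 2 = 4. LR is z²(treatment × t²) + z²(common t²). With a linear common trend the chance is P(χ² on 2 df > 4) = e⁻² = 13.5%. Curvature is expressed as the chi-square noncentrality of the common t² term. The table uses 400,000 draws per setting, with ranges over the five V.

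| Common trend | AIC picks quadratic | Two-sided error (nominal 5%) | False benefit (nominal 2.5%) |
|---|---|---|---|
| Linear (0) | 14% | 5.9-7.3% | 3.0-3.6% |
| Curved (2) | 39% | 6.9-9.3% | 3.4-4.7% |
| Curved (6) | 75% | 8.0-11.7% | 4.0-5.9% |

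If the quadratic were always used, two-sided error would be 8.7-13.2%.

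**Step 3, which gap matters.** These variants keep the rest of the setup:

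- AIC, then Holm over the five visits: 2.8-5.1%.
- AIC, then month 24 only: 5.0-5.5%.
- Fixed linear interaction, no selection: 4.9-5.1%.
- BIC, uncorrected: 5.0-5.2%, 5.1-6.1% and 5.8-8.3% for the three trends.
- A 5% likelihood-ratio test, uncorrected: 5.5-6.0%, 6.1-7.7% and 7.5-10.4%.

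Choosing the model from the data adds little by itself. The inflation comes mainly from the open set of visits without a correction.

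**Step 4, check by fitting the model.** 1000 null data sets per scenario were simulated from a random-intercept adjacent-category model (120 subjects) and analysed with the same AIC rule. Two-sided error was 6.7% with a linear trend: 13.7% chosen × 21.9% error = 3.0 points from the quadratic branch, and 3.7 from the linear branch. With a curved trend it was 12.1%: 77.3% × 14.5% = 11.2 points, and 0.9. The fixed interaction gave 3.9-4.3%. Bonferroni at 0.05/5 = 0.01, with the quadratic always used, gave 3.2-3.4%.

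**The case against.** The strongest reply is that the plan does commit to correcting for multiple comparisons, and that the 6-12% arises only if this commitment is ignored. With Holm, the same setup stays at or below about 5%. This stands. A reader might infer from the figures that the plan runs Aim 1 at up to 12% error. The documents do not support that, because a suitable correction chosen later could still hold the level. They only leave it undecided.

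It is also fair that AIC, the degree of curvature and one visit sufficing are assumptions, and that BIC is milder.

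A third point is that the linear interaction is not the only sound primary test. The plan provides for non-linearity on purpose. Placebo participants who convert to diabetes are started on metformin (Study Procedures, k), so the arm difference could narrow late, where a linear test is weak. This stands too, and the fix allows for it.

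Lastly, the abstract calls the trial a pilot. That lowers the stakes, but the plan still states significance-based success rules, power and a 5% level for Aim 1.

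**Conclusion.** The point holds in this form: the Aim 1 success rule depends on a data-driven model choice, its non-linear branch names neither visits nor a correction, and no other section secures the two-sided 5% level of 3.D.3. The level is unsecured, not shown to be violated.

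Two-sided error is about 6-12% if AIC selects the model, any of five visits counts and nothing is corrected. It is at or below about 5% with Holm, and about 5% with one fixed test. The range rests on the covariance structures and curvatures tried. That the rule is open rests on the text alone. This should be fixed before outcomes by arm are seen; a few sentences suffice.

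**What to change.** Before anyone finalising the SAP sees outcome data by arm:

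1. Name one primary Aim 1 test at two-sided 5% that applies whatever the fit comparison shows, and claim benefit only if its direction favours metformin. The default is the 1-df linear treatment-by-time interaction already in the Overview. If non-linearity is a concern, a 2-df joint test of the treatment-by-time and treatment-by-time-squared terms, or a single month-24 contrast, would also hold the level.
2. Make the other model and the visit-specific contrasts supportive, with Holm over a listed set of visits.
3. State which frailty assessments enter the model. Reconcile the six-monthly schedule with its 3-month repeats, the assessment at diabetes conversion that can replace month 12 or 24, and the visits table with its month-3 entry.

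**Cost.** SAP wording, plus a power trade-off. Suppose the linear test has 86% power for a linear effect; this is an assumption, because 3.D.3 powers an overall odds ratio on the frailty score and does not clearly power this interaction. The noncentrality is then (1.960 + 1.080)² = 9.24, and the 2-df test has 78% power for the same effect. Keeping the linear month-24 effect size:

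- Reached by month 12 and held: 86-88% for the 1-df test.
- Reached by month 3 and held: 43-65% for the 1-df test.
- Reached at month 12, then halved by month 24: 34-38% for the 1-df test, 68-89% for the 2-df test.

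The choice should follow the expected shape of the effect and be recorded with its reason.

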k) Management of conversions: Any one of the following will prompt 2-hour OGTT to confirm possible diagnosis of diabetes: fasting glucose  $\geq$  126 mg/dL, HbA1c  $\geq$  6.5%, 2-hour OGTT glucose of  $\geq$  200 mg/dL, or clinical signs and symptoms of diabetes. If any of these occur, OGTT will be conducted within 6 weeks. If the subsequent 2-hour OGTT glucose is  $\geq$  200 mg/dL, diabetes conversion will be confirmed. If diabetes conversion occurs based on the OGTT, measurements of frailty, insulin sensitivity (clamp), body composition (DEXA), coagulation tests, stool sample, and inflammation (muscle and systemic) will be

performed. If these assessments are conducted within 1 month of the 12 month or 24 month assessments, the 12 or 24 month assessments will not be conducted. After these repeat measurements are performed, the study allocation will be unblinded, and, if receiving placebo, subjects will be initiated on metformin and titrated as above. Medication management will occur by an independent practitioner (MD or NP) on the study staff who is not the PI such that the PI will remain blinded to study treatment. Hemoglobin A1c will be monitored in those who have converted to diabetes, and, if it reaches  $\geq 7.5$ , subjects will be initiated on 15 mg pioglitazone in addition to metformin unless there is a contraindication to pioglitazone. The rationale for adding pioglitazone versus other antidiabetic agents is that the low dose metformin-thiazolidinedione combination has been shown to have a potent effect to prevent diabetes (Zinman et al., 2010). Pioglitazone will be increased to 30 mg if hemoglobin A1C remains  $\geq 7.5$ . Pioglitazone will not be initiated in any subject with the following: hematuria, history of bladder cancer, lower extremity edema  $> 1+$ , or known history of osteopenia or osteoporosis. Subjects will be seen every 3 months for monitoring of HbA1C. If maximal metformin (1000 mg BID) and pioglitazone (30 mg daily) doses are reached (or if the patient cannot tolerate metformin and/or pioglitazone) and HbA1C remains  $\geq 8$ , subjects will be referred to their primary care physicians for further treatment, but will remain in the study for frailty assessment and all other follow-up studies. Subjects who initially were on metformin will receive pioglitazone 15 mg (in addition to metformin) if Hemoglobin A1c reaches  $\geq 7.5$ , which will be titrated to 30 mg if necessary as described above.

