
6. Questionnaire data collection. Various standardized questionnaires will be used to obtain information relative to these analyses, including some information needed to ascertain frailty (physical activity level and self-reported exhaustion), a depression scale, and screen for cognitive impairment (Tariq et al., 2006). These are minimal risk to the participant but could result in mild psychological distress which should be transient and resolve. To minimize this risk, study personnel will be sure to inform participants that he/she can skip any question he/she prefers not to answer. All of the questions in the interview will be performed by a trained staff member or the PI, who is a geriatrician, to assure risks are minimal as would be the case in standard clinical care.

7. Administration of metformin. The administration of metformin in adults with normal renal function is safe, the inclusion/exclusion criteria have been tailored so as to reduce the possibility of adverse events. The most severe adverse event associated with metformin use is lactic acidosis which is very rare (occurs in < 1%), and is more common in patients with impaired renal function. Therefore, individuals with creatinine clearance <45 mL/min are excluded from this study based on FDA dosing recommendations. More common adverse reactions (occur in > 10%) are diarrhea, nausea, and vomiting. Subjects will be provided with the common side effects as part of informed consent and will be monitored closely throughout the study. The medication will be titrated to the maximum tolerable dose. Subjects who do not tolerate metformin will be disenrolled.

8. **Administration of pioglitazone.** Only subjects who convert to diabetes and whose hemoglobin A1C is over  $\geq 7.5$  despite metformin administration will receive pioglitazone. Subjects with hematuria on urinalysis or history of bladder malignancy will not be administered pioglitazone. Subjects with liver disease and elevated transaminases are excluded from the study. More common adverse reactions (occur in  $> 10\%$ ) are edema and upper respiratory tract infection. Patients will be evaluated with routine history and physical examinations to monitor for adverse reactions, and those with peripheral edema greater than 1+ or any evidence suggestive of heart failure will not receive pioglitazone.

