Lipids, blood pressure	X	X
Fasting glucose, HbA1c, Insulin Sensitivity from OGTT (Matsuda) and Insulin Clamp	X	X
Inflammation (systemic & muscle), Insulin Signaling (muscle)	X	X
Diabetes conversion		X
Pioglitazone use		X

Of secondary interest, a per protocol analysis will be carried out with restriction to patients who follow the protocol throughout the study, and where those who drop out, violate the protocol or change treatments are excluded. Separately, those who change treatments will be summarized and described. To account for any treatment change, we will also consider principal stratification analysis (which requires categorization of patients based on treatment change patterns) and marginal structural modeling (which obtains the overall metformin effect accounting for treatment change, and time-varying covariates (e.g., diabetes status), and outcomes (e.g. frailty, physical function) history.

Metformin dose will be handled in the statistical analysis by conducting dose-response analysis among metformin users. Several options of metformin dose/exposure variables will be considered in separate analyses: average daily dose, clinical meaningful threshold for average daily dose, total days of supply, and clinical meaningful threshold for total days of supply. Should there be any discrepancy among these dose-response analyses, we will reconcile these results for the final interpretation.

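### The secondary per-protocol rule excludes placebo-arm diabetes converters but, by default, keeps metformin-arm converters, so its exclusions differ by arm and are related to outcome

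*Combined protocol and SAP*

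**What the plan says.** The analysis rule and the conversion rule stand in different parts of the document.

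- **Statistical Methods & Power Calculations, Overview.** For both aims, "primary inference will be drawn based on intention to treat (ITT) analyses". On the secondary set, the plan says: "Per protocol analyses will be used to inform the metformin effect among completers". Below Table 7 the set is defined as patients who follow the protocol throughout, "where those who drop out, violate the protocol or change treatments are excluded". Changing treatment is listed separately from violating the protocol. Those who change are to be summarised separately, and "we will also consider principal stratification analysis" together with marginal structural modelling.
- **Item 6, Study Procedures, k) Management of conversions.** At confirmed conversion, frailty and the mechanistic measures are taken first. Then "the study allocation will be unblinded, and, if receiving placebo, subjects will be initiated on metformin and titrated as above". For the other arm: "Subjects who initially were on metformin will receive pioglitazone 15 mg (in addition to metformin) if Hemoglobin A1c reaches" the threshold of 7.5. Conversion alone does not alter the metformin arm's drug.
- **Potential risks, item 7 (Administration of metformin).** "Subjects who do not tolerate metformin will be disenrolled".

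The plan does not say whether a switch that the protocol itself directs, or a pioglitazone add-on, is a change of treatment for the per-protocol set.

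**The concern.** The same clinical event has different consequences for the analysis set in the two arms. A placebo participant with confirmed diabetes must switch drug and so loses all data, including visits before conversion. A metformin participant with confirmed diabetes keeps the assigned drug and stays in, unless something further happens.

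The event is related to the outcome on the protocol's own premise. Preliminary Data reports an odds ratio of 1.84 for gaining a frailty characteristic with diabetes. The Aim 2 rationale names slower progression to diabetes as one route by which metformin might act. The rule therefore takes likely worseners out of the comparator and removes that route from one arm only. A gap between the per-protocol and intention-to-treat results could then reflect the exclusion rule and be taken for something about the drug.

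**Working it through.** The plan gives no figure for the per-protocol set, so there is none to reproduce. The check sizes this one mechanism.

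**Inputs from the document**
- Odds ratio for gaining a frailty characteristic with diabetes: 1.84, 95% CI 1.02–3.33 (Preliminary Data, obesity, pre-diabetes and diabetes in SALSA).
- Reduction in diabetes onset on metformin: 31% over 2.8 years, so relative risk 0.69 (Background, role of metformin).
- Projected worsening of frailty: 47–58% (Research Design and Methods, before Aim 2).
- Completers: 60 per arm (section 3.D.3).

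**Assumptions**
- Two-year placebo conversion rate *c* is not given; 10%, 20% and 30% are shown.
- Worsening in non-converters, p0 = 0.50.
- No direct drug effect on frailty.
- All metformin converters retained.

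**Step 1. Risk in converters.** Odds = 1.84 × 0.50/0.50 = 1.84, so p1 = 1.84/2.84 = 0.648.

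**Step 2. Per-protocol risks.** Placebo (non-converters only) = p0 = 0.50, odds 1. Metformin (everyone) = p0(1 − 0.69c) + p1(0.69c). At c = 20%, 0.69c = 0.138, and the risk is 0.50 × 0.862 + 0.648 × 0.138 = 0.520. The odds ratio is 0.520/0.480 ≈ 1.09 (1.085 unrounded).

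**Step 3. All converters kept in both arms.** The placebo risk at c = 20% becomes 0.50 × 0.80 + 0.648 × 0.20 = 0.530, and the odds ratio is 0.96.

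| Assumed placebo conversion | OR, plan's per-protocol rule | OR, converters kept in both arms |
|---|---|---|
| 10% | 1.04 | 0.98 |
| 20% | 1.09 | 0.96 |
| 30% | 1.13 | 0.95 |

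Setting p0 to 0.47 or 0.58 leaves the middle column at 1.04, 1.08–1.09 and 1.13. At 20%, 0.20 × 60 = 12 placebo participants leave, while about 0.138 × 60 ≈ 8 metformin converters stay.

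**Step 4. Sensitivity at 20% conversion**
- Diabetes odds ratio at its confidence limits, 1.02 and 3.33: per-protocol OR about 1.00 and 1.16.
- Pioglitazone counted as a change, with 25%, 50% or 100% of metformin converters receiving it: 1.066, 1.045 or 1.000. The last case empties both arms of converters and the shift disappears, so in this model the asymmetry is its source.
- Intolerance disenrolment of 5%, 10% or 15% of the metformin arm (assumed rates; overall placebo worsening 52.5%): 1.054, 1.023 or 0.993 if those removed have odds ratio 1.84 for worsening; 1.033, 0.981 or 0.931 if it is 3.0.

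**Step 5. Size against noise.** With 60 and 48 participants and about 50% worsening, SE(log OR) ≈ √[1/(60 × 0.25) + 1/(48 × 0.25)] = √(0.0667 + 0.0833) = 0.39. The shift is ln(1.085)/0.39 = 0.082/0.39 ≈ 0.2 SE.

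**The case against.** The strongest reply is that the plan already protects itself. Intention to treat is primary, an average complier effect is planned, treatment changers are described separately, and diabetes conversion and pioglitazone use are time-varying covariates in Table 7. The marginal structural model would take diabetes status into account. This stands as far as primary inference goes. It does not repair the per-protocol analysis, which is a firm commitment with a stated interpretation, whereas principal stratification and marginal structural modelling are only to be considered.

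Three stronger readings are tempting, and the documents do not support them.

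- **That the per-protocol estimate is, on balance, biased against metformin.** Only this mechanism has that direction. Metformin-intolerant subjects are disenrolled, and if they are frailer the net bias could be cancelled or reversed, as step 4 shows.
- **That metformin converters are certainly kept and nothing changes for them.** The status of pioglitazone is undefined, and confirmed converters in both arms are unblinded.
- **That the analysis would show harm where intention to treat shows benefit.** At this sample size, odds ratios of 1.09 and 0.96 could not be told apart.

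It is also fair to say that the inputs are borrowed. The 1.84 comes from a cohort with established diabetes, not conversions found by scheduled glucose testing within two years. The 31% was observed over 2.8 years. Finally, any rule that uses conversion conditions on an event after randomisation, so a symmetric rule is better but not free of bias.

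**Conclusion.** The concern holds as a defect in how a secondary analysis set is defined. Read together, the exclusion rule and the conversion rule remove placebo converters entirely and, by default, leave metformin converters in. That is differential exclusion on an event that the protocol links to the outcome. No stated definition avoids it, since following the protocol does not rescue a participant who changes treatment.

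The size is modest: 1.04 to 1.13 across the assumed conversion rates, and 1.00 to 1.16 at 20% over the uncertainty in the diabetes odds ratio. These figures rest on an assumed conversion rate, no direct drug effect and external odds ratios. They describe one mechanism and do not predict the net bias. What does not survive is the plan's reading of this set as showing the metformin effect among completers. The point should be settled before analysis.

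**What to change.** Replace whole-participant exclusion for converters with one rule for both arms. In the per-protocol analysis, keep each participant's data up to and including the conversion assessment, and censor at confirmed conversion whichever arm the participant is in. State that this rule, and not any later pioglitazone, governs converters. Management of conversions already places the frailty assessment before unblinding and rescue, so no new data or visits are needed.

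The SAP should state the cost openly. The estimate becomes an effect before conversion, drops later visits in both arms, and censors on an event that treatment affects. It should therefore rest either on the likelihood analysis under missing at random (section 3.D.7), conditioning on observed glycaemic and frailty history, or on inverse-probability weighting through the marginal structural model that the plan already names. It should be labelled accordingly and not reported as the overall metformin effect among completers. Disenrolment for intolerance should be tabulated by arm beside it, because this rule does not address that source of bias. The change is a few sentences of SAP wording, plus the weighting model if that route is chosen.
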